3.1 General Design

This is an open labeled phase II study of vitamin B₃-amide dietary supplementation in pregnant women with early-onset preeclampsia, per ACOG guidelines. We will enroll 24 pregnant women at 24-33 weeks 3 days with EOP and anticipated treatment by expectant observation. If the woman is anticipated to remain undelivered for 48 hours after diagnosis she will receive vitamin B₃-amide, 2.5 mg/day dosed in the following manner: administered as 1000mg at 8AM and 12MN; 500mg at 4PM, continuing until delivery or 34 weeks, whichever occurs first. Optional research blood samples will be collected at times of clinically indicated blood draws (baseline and 2-3 times per week) to measure nicotinamide and its metabolite 2-pyridone, sFlt-1 and PIGF. A sample of cord blood will be collected (6ml) following delivery.

All study subjects will receive standard surveillance and treatment for expectant management of EOP, which may include but is not limited to:

- Daily prenatal vitamin
- 24-hr urine collection for protein excretion at admission
- Blood sampling for hematologic, liver, and kidney function at time of diagnosis and every 2-3 days thereafter
- Magnesium sulfate for seizure prophylaxis
- Betamethasone to accelerate fetal lung maturity
- Antihypertensive agents
- Twice weekly fetal surveillance by NST (30 minutes of continuous fetal heart rate monitoring) or BPP (30 minutes of ultrasound to monitor for fetal breathing, movement, fluid)
- Weekly ultrasound to measure amniotic fluid and UA Dopplers

In addition to above standard care for EOP, subjects will receive surveillance and treatment solely for study purposes, including:

- Daily administration of vitamin B₃-amide, 2.5 Gm/day in 3 divided doses; "on treatment" is defined as within 24 hours of dose
- Daily (M-F) study staff visit to query side effects if in-patient; with each outpatient visit (typically twice a week) if discharged from the hospital
- Optional blood sampling to coincide with clinical blood draws to measure sFlt-1, nicotinamide and 2-pyridone levels; chart abstraction to review liver function testing results (done clinically)
- Chart abstraction for maternal and delivery data (up until maternal discharge) and neonatal data (until 30 days of age or until discharge, whichever occurs first). We will

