3.2 Study Outcomes

PRIMARY

- Maternal mean arterial blood pressure, defined as the highest MAP within 24 hour period

SECONDARY-SAFETY AND TOLERABILITY

- Liver toxicity, defined as 3x ULN of ALT or AST within 24 hours of study drug
- Maternal report of side effects
- Clinical parameters of maternal and fetal well being
- Composite neonatal outcome

Maternal or Fetal Parameter	Safety Endpoint
History	Headache unrelieved by oral analgesics
Physical examination	Abdominal tenderness, (right upper quadrant or epigastric)
Vaginal bleeding	Fall in hematocrit of $\geq 3\%$
Urine output	Oliguria (< 500 cc/24 hr)
Serum LFTs	AST and/or ALT $\geq 3x$ ULN within 24 hours of study drug
Fetal NST (or BPP)	Category III (or < 6)

SECONDARY-PHARMACOKINETICS

- Nicotinamide and metabolite concentrations in plasma at baseline, 2, 8, and 24 hours
- Peak plasma drug and metabolite concentration and time to reach peak
- Nicotinamide and metabolite elimination half-life
- Nicotinamide and metabolite area under the curve (integral of the plasma concentration-time curve)
- Nicotinamide and metabolite concentrations in urine at baseline, 8 and 24 hours

4 Subject Selection and Withdrawal

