5.5 Prior and Concomitant Therapy

Subjects will have clinical treatment decisions made by the primary physician, independent of study participation. All subjects will receive standard care as noted below:

- Daily prenatal vitamin
- Blood sampling for hematologic, liver, and kidney function at enrollment and every 2-7

- days thereafter
- Magnesium sulfate for seizure prophylaxis
 - Betamethasone to accelerate fetal lung maturity
 - Antihypertensive agents as needed, determined by primary clinician
 - At least biweekly fetal surveillance by NST (30 minutes of continuous fetal heart rate monitoring) or BPP (30 minutes of ultrasound to monitor for fetal breathing, movement, fluid)
 - Weekly ultrasound to measure amniotic fluid and UA Dopplers

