6.2 Study intervention and procedures for participants with early onset severe preeclampsia

The respective pharmacy will dispense vitamin B₃-amide, which will be administered given to the subject by study staff if out-patient or by in-patient nursing staff if in-patient. Study staff will meet with subjects at each prenatal visit or daily [(M-F) if in the hospital] to discuss compliance and side effects.

Clinical care will continue per recommendations of primary obstetrician caring for the patient. Standard procedures may include:

- 24-hr urine collection for protein excretion at admission
- Blood sampling for hematologic, liver, and kidney function at enrollment and every 2-3 days thereafter
- Physical examination by primary clinical provider
- Weight and intake/output measurement as ordered by primary clinical provider
- Magnesium sulfate for seizure prophylaxis
- Betamethasone to accelerate fetal lung maturity
- Antihypertensive agents
- Daily fetal surveillance by NST (30 minutes of continuous fetal heart rate monitoring) or BPP (30 minutes of ultrasound to monitor for fetal breathing, movement, fluid)
- Weekly ultrasound to measure amniotic fluid and UA Dopplers

The primary obstetrician will make decisions regarding indication and timing of delivery. Clinical management of the infant after delivery will be per standard treatment dictated by the neonatologist caring for the baby.

Study procedures include:

- Daily administration of vitamin B₃-amide, 2.5Gm given as administered as 1000mg at 8AM and 12MN; 500mg at 4PM
- Daily (if in-patient) or with each prenatal visit (if out-patient) study nurse visit to query side effects
- Optional blood sampling to coincide with clinical blood draws to measure nicotinamide and 2-pyridone, sFlt-1 and PIGF levels
- Optional blood sampling for Nicotinamide levels at the following times:
 - Day 1 - Baseline – pre 1st dose; Peak – 2 hrs post 1st dose; Trough – pre 2nd dose
 - Day 3 – Trough – pre AM dose; Peak – 2 hrs post AM dose
 - Day 7 - Trough – pre AM dose; Peak – 2 hrs post AM dose
 - Cord blood following delivery.
- Chart abstraction to review maternal liver function testing results, delivery data (up until discharge) and neonatal data (until 30 days of age or until discharge, whichever occurs

first)

6.2a Study intervention and procedures for healthy pregnant and non-pregnant controls

- Administration of a single dose (1000mg) of Nicotinamide at 8AM.

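### The liver-toxicity proportion omits rises first measured more than 24 hours after a dose, no LFT is tied to the last dose, and Section 7.1 plans no count of what is left out

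*Combined protocol and SAP*

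**What the plan says.** The outcome in Section 3.2 is "Liver toxicity, defined as 3x ULN of ALT or AST within 24 hours of study drug". The same 24-hour limit appears in the Study Summary, in the comparison with an expected 20% (Section 7.1), and in the study and individual stopping rules (Sections 4.4.1 and 8.4).

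The protocol orders no LFTs for this outcome in the preeclampsia group. Sections 3.1 and 6.2 take results of clinical tests from the chart. The sampling interval is stated three times:

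- Section 3.1: "Blood sampling for hematologic, liver, and kidney function at time of diagnosis and every 2-3 days thereafter"
- Section 6.2: "Blood sampling for hematologic, liver, and kidney function at enrollment and every 2-3 days thereafter"
- Section 5.5: "Blood sampling for hematologic, liver, and kidney function at enrollment and every 2-7" days

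Sections 3.1 and 6.2 introduce their lists as care that may be given. Section 5.5 says that all subjects will receive what it lists. No section requires an LFT at or just after the last dose.

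The regimen is "administered as 1000mg at 8AM and 12MN; 500mg at 4PM". Sections 3.1, 5.2 and 8.4 continue it to delivery or 34 weeks, whereas Section 4.4.1 stops it at delivery or two weeks.

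**The concern.** The counting window is 24 hours and every stated LFT interval is longer. A woman can have normal LFTs at her last on-treatment draw, develop a rise while still on drug, stop treatment, and be sampled next at 30 hours. Her result is not liver toxicity under the plan, although the rise began on treatment.

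Section 8.1 calls liver toxicity the most serious risk of the agent. Such a case leaves three things at once: the reported proportion, the comparison with 20%, and the study stopping rule. Section 7.1 plans no table in which it would reappear. How many cases are lost depends on how often clinicians sample near the end of treatment, which the protocol does not control and describes inconsistently.

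**Working it through.** The plan gives no power, precision or derivation for the liver proportion or its 20% reference, so there is no figure of its own to reproduce. The inputs are the 24-hour window (3.2), the dosing times (6.2), draw intervals of 2, 3 and 7 days (3.1, 5.5, 6.2) and 24 women (7.1; the Study Summary says 25).

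**1. Draws during dosing.** Doses at 8 AM, 4 PM and midnight are 8 hours apart. Since 8 < 24, every draw during uninterrupted dosing counts, as does any draw up to 24 hours after the last dose.

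**2. Women with no scheduled draw in the closing 24 hours.** Assume that treatment stops at a random point in a draw cycle of k days. Then P(no draw within 24 hours) = 1 − 1/k:

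- k = 2: 1 − 1/2 = 0.50
- k = 3: 1 − 1/3 = 0.67
- k = 7: 1 − 1/7 = 0.86

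**3. Share of on-treatment rises missed.** This is a different quantity. Assume scheduled draws every k days from baseline, a constant hazard of crossing 3x ULN on drug, a rise that persists, and treatment duration T uniform over a range. The last countable draw is at L = k × floor((T + 1)/k), and the uncovered time is m = max(0, T − L). The missed share is the sum of m divided by the sum of T.

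Example with k = 3 and T from 2 to 7 days: time is uncovered for T from 3 to 5 (integral 2.0) and from 6 to 7 (integral 0.5). The denominator is (49 − 4)/2 = 22.5, so the share is 2.5/22.5 = 0.111.

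| Draw interval | T 2-7 d | T 2-14 d | T 7-14 d | T 2-28 d |
|---|---|---|---|---|
| 2 days | 6.7% | 3.1% | 2.0% | 1.7% |
| 3 days | 11.1% | 8.3% | 7.5% | 4.2% |
| 7 days | 71.1% | 35.4% | 24.5% | 17.9% |

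The duration ranges are assumptions, because the documents give no distribution. Short courses are plausible: Section 1.1 reports that 75% of women with early-onset disease and a high sFlt-1/PlGF ratio deliver within one week.

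**4. Effect on the stopping rule.** With 24 women, 20% is 4.8, so more than 20% means at least 5 cases. If the true rate is p and a share s is missed, the count is Binomial(24, p(1 − s)). The chance of at least 5, in a single look at full enrolment with p assumed, is:

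| True rate p | s = 0 | s = 10% | s = 30% | s = 50% |
|---|---|---|---|---|
| 20% | 0.54 | 0.44 | 0.24 | 0.09 |
| 30% | 0.89 | 0.82 | 0.59 | 0.29 |
| 40% | 0.99 | 0.97 | 0.84 | 0.54 |

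With 25 women the threshold is 6 cases. At p = 30% the row becomes 0.81, 0.70, 0.43 and 0.16.

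**The case against.** The window is a deliberate, prespecified on-treatment definition. Section 1.1 lists raised liver enzymes as a feature of preeclampsia, so a limit near dosing helps keep postpartum disease out of the count. That stands, and it is why the definition should stay.

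Late rises are also not lost to the trial. Under Section 8.1 a laboratory abnormality suggesting organ toxicity is an adverse event with no 24-hour limit, the maternal reporting period runs to hospital discharge, and Section 3.1 adds a call 30 days after stopping. This stands as to capture. It does not return the cases to the liver proportion, and a telephone call does not measure ALT.

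The random-stop assumption is weak. Draws follow clinical need, so extra ones around delivery would reduce the loss, and a woman stopped for LFTs at or above 3x ULN within the window has a countable draw by construction. The figures are therefore illustrations.

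A reader might infer three stronger things that the documents do not support:

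- That 50-86% of toxicities are missed. Those figures describe women without a scheduled draw in the closing window. The 86% also needs weekly draws, which only Section 5.5 allows.
- That every rise found after the last dose is excluded. Those drawn within 24 hours count.
- That the rate is simply biased low. Disease-related rises on drug are counted too, while Section 8.1 puts drug liver toxicity below 1%. As a measure of drug-caused toxicity, the net direction is unclear.

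**Conclusion.** The point holds in limited form. The plan excludes rises that begin on drug after the last on-treatment draw, or during a dose interruption, and are first measured more than 24 hours after a dose. For treatment-emergent rises this is under-counting. Under the stated model it is modest with draws every 2-3 days (about 2-11% of such rises) and substantial with weekly draws (18-71%, the upper end for courses of 2-7 days). At an assumed true rate of 30% in 24 women, missing 10% lowers the chance of crossing the stopping threshold from 0.89 to 0.82.

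No single corrected rate can be given, because the documents supply neither the distribution of treatment duration nor the time course of LFT rises. The comparison with 20% has a further weakness: that reference has no stated window, so it may not match a 24-hour rate.

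**What to change.** - Keep the 24-hour definition. Add to Section 7.1 a prespecified supplementary count of women with any ALT or AST at or above 3x ULN from first dose to maternal discharge. Split it by within or beyond 24 hours of a dose and by before or after delivery. Specify that discharge means discharge after delivery, because Section 5.4 lets women go home on therapy.
- Beside each count, give the number of women who had an LFT in that window, so that absence of cases can be told from absence of tests.
- State which window the 20% reference refers to.
- Reconcile the LFT interval in Section 5.5 with Sections 3.1 and 6.2. Also reconcile the treatment duration in Section 4.4.1 with Sections 3.1, 5.2 and 8.4, since it determines when the window closes.

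The cost is one table from chart LFTs that are already abstracted, with no new tests. It will include some disease-related postpartum rises, which the split makes visible. It still depends on how often clinicians sample, and it leaves the stopping rule as written.

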4.1 Inclusion Criteria for participants with early-onset preeclampsia

1. Maternal age 18-45 years
2. Singleton or twin pregnancy with no known fetal anomalies
3. Early-onset preeclampsia OR early-onset severe gestational hypertension
 - a. Early onset defined as 24-33 weeks 3 days gestation
 - b. Preeclampsia defined as new onset hypertension and proteinuria: systolic BP ≥ 140 mm Hg and/or diastolic BP ≥ 90 mm Hg on two occasions 6 hours apart and > 300 mg proteinuria on 24 hour urine collection OR urine P/C ratio > 0.3 ;

- c. Or BP \geq 160 mm Hg and/or diastolic BP \geq 105
- d. Dating criteria based on menstrual dating confirmed by first or second trimester ultrasound OR second trimester ultrasound if menstrual dating unavailable;
- e. Deemed clinically stable by primary clinician and candidate for expectant management (delayed delivery) for at least 48 hours;
- f. Dating criteria based on menstrual dating confirmed by first or second trimester ultrasound OR second trimester ultrasound if menstrual dating unavailable;
4. Deemed clinically stable by primary clinician and candidate for expectant management (delayed delivery);
5. Pre-existing medical diseases such as hypertension, diabetes, endocrine disorders, gastrointestinal diseases, are well controlled
6. Maternal liver function tests $<$ 2x ULN
7. Maternal platelet count \geq 100,000 mm³
8. Fetal well-being established by estimated fetal weight \geq 5th %tile; normal amniotic fluid volume (MVP \geq 2 cm); normal UA Dopplers; AND reactive NST or BPP $>$ 6
9. Plan for expectant management until delivery
10. Delivery not anticipated within first 48 hours

4.2 Exclusion Criteria for participants with early-onset preeclampsia

1. Preeclampsia $<$ 24 or \geq 33 weeks 4 days gestation;
2. Multiple gestation;
3. Suspected fetal structural or chromosomal abnormality;
4. Pre-existing renal disease (creatinine \geq 1.5 mg/dL)
5. Plan for delivery within 48 hours
6. Any pre-existing medical condition that would increase risk for liver toxicity (e.g. hepatitis B or C; HIV)
7. Eclampsia; cerebral edema on CT/MRI; headache unresolved with analgesics
8. Pulmonary edema
9. HELLP syndrome
10. Evidence of liver dysfunction (LFTs \geq 2x ULN)
11. Thrombocytopenia (platelets $<$ 100,000 mm³)
12. Evidence of fetal compromise: EFW $<$ 5th percentile; BPP $<$ 6; absent or reverse diastolic UA blood flow; oligohydramnios (MVP $<$ 2 cm)
13. Placental abruption defined as unexplained vaginal bleeding
14. Preterm labor defined as regular contractions and cervical change
15. Any condition deemed by the investigator to be a risk to mother or fetus in completion of the study
16. Any condition deemed by the investigator to require delivery within 48 hours

4.1a Inclusion Criteria for healthy, normotensive, pregnant women

- Maternal age 18-45 years
- Singleton or twin pregnancy with no known fetal anomalies (24 weeks to 33 weeks 3 days)
- No known medical complications

4.2a Exclusion Criteria for healthy, normotensive, pregnant women

- Current cigarette smoker
- Hypertension requiring medical treatment
- Diabetes requiring medical treatment
- Pre-existing renal disease (creatinine \geq 1.5 mg/dL)

- Any pre-existing medical condition that would increase risk for liver toxicity (e.g. hepatitis B or C; HIV; INH use)
- Currently taking medication for a chronic medical condition
- Currently taking an oral or IV antibiotic or antifungal medication

4.1b Diagnosis and Inclusion Criteria for healthy nonpregnant women

- Age 18-45 years
- No known medical complications or disease (eg hypertension, diabetes, liver or kidney disease)

4.2b Exclusion Criteria for healthy nonpregnant women

- Current cigarette smoker
- Hypertension requiring medical treatment
- Diabetes requiring medical treatment
- Pre-existing renal disease (creatinine \geq 1.5 mg/dL)
- Any pre-existing medical condition that would increase risk for liver toxicity (e.g. hepatitis B or C; HIV; INH use).
- Currently taking medication for a chronic medical condition (excluding oral contraceptives)
- Currently taking an oral or IV antibiotic or antifungal medication

4.3 Subject Recruitment and Screening

Study personnel will review in-patient records or prenatal records under a limited waiver of HIPAA granted by the Institutional Review Board to determine if a patient meets eligibility requirements. If eligible, study personnel will approach medical provider to determine appropriateness of patient to serve as a study subject. If appropriate, study personnel will invite the patient to serve as a study subject.

Study personnel will describe the study in detail and review the study protocol with the patient. Women agreeing to participate will sign a consent form; one copy will be placed in their medical record, and a copy will be given to the patient for her records.

4.4 Early Withdrawal of Subjects

4.4.1 When and How to Withdraw Subjects

Subjects may withdraw at any time and for any reason. Subjects may be withdrawn if they no longer meet eligibility criteria; or if in the opinion of the investigator it is not in the subject's best interest to continue. A subject may also be withdrawn if she experiences an unmanageable or irreversible adverse Grade 3 or 4 adverse event using the CTCA v3.0 criteria as defined in section on safety monitoring. The date of withdrawal from study participation will be recorded in the CRF. Subjects who either complete or are removed from the treatment phase at any time will have complete data chart abstracted and recorded for study purposes.

Specific study stopping rules include:

- Any maternal or fetal death deemed to be related or possibly related to study participation
- More than expected prevalence of liver toxicity within 24 hours of study drug, thus > 20% of subjects experience liver toxicity (more than 1 subject for every 5 subjects enrolled)
- More than expected prevalence of fetal side effects (defined as BPP < 6 OR UA Dopplers show absence or reversal of diastolic blood flow), (more than 1 delivery for fetal reasons per every 5 subjects enrolled)

Specific rules to stop study intervention for individual subject

- Delivery, or two weeks of treatment (“on-treatment” defined as within 24 hours of study drug)
- Liver toxicity (LFTs \geq 3x ULN within 24 hours of study drug)
- Maternal side effects that cannot be managed with oral medication

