
Statistical Methodology
	
Primary Outcome
 
• Mean arterial blood pressure before, 48 hours, and 7 days after daily dosing 
Secondary Outcomes
 
• Maternal liver toxicity: the proportion of women who develop elevated liver function tests (ALT and/or AST \geq 3x ULN within 24 hours of study drug) will be determined and compared to expected proportion of 20%• Maternal side effects (nausea, vomiting, rash, headache)• Optional: Plasma nicotinamide and 2-pyridone levels; sFlt-1 and PIGF levels

1. Introduction

This document is a protocol for a human research study. This study is to be conducted according to US and international standards of Good Clinical Practice (FDA Title 21 part 312 and International Conference on Harmonization guidelines), applicable government regulations and Institutional research policies and procedures.

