- Blood sampling at baseline (pre-dose), 2 hours post dose, 8 hours post dose and 24 hours post dose.
- Urine sample at baseline (pre-dose), 8 hours post dose and 24 hours post dose.
- This will be done either in the clinic or the CTRC

6.3 **Laboratory specimen handling procedures**

Blood for research purposes will be collected at the time of clinically indicated blood draws. Specimens will be labeled with the subject's unique study ID and processed.

Specimens to be tested for circulating sFlt-1 and PlGF levels will be stored and shipped as a single batch on dry ice to the research laboratory at Harvard University. The interassay coefficient of variance for sFlt1 and PlGF immunoassays ranges from 2.6% to 3.0%.

Specimens collected for nicotinamide and 2-pyridone measurements will be sent to the UNC School of Pharmacy Lab ([name]). [name] developed a LC-MS/MS method using protein precipitation (acetonitrile) to measure nicotinamide and 2-pyridone during our previous phase I study.

7 **Statistical Plan**

7.1 **Statistical Methods**

Sample size: The study sample size was calculated to the primary outcome of MAP. We stipulated *a priori* that $\alpha = .05$ and $\beta = 0.2$. Using the highest BP measured within each 24-hr period and applying the following formula we will calculate daily MAP:

$$\text{mean arterial BP} = [2(\text{diastolic BP}) + \text{systolic BP}] \div 3$$

Assuming that the mean (\pm sd) MAP at enrollment of our subjects is 107 (\pm 10) mm Hg, to detect a difference from enrollment to 48 hours after treatment of 7 mm Hg in MAP requires that 20 subjects be enrolled. We will enroll 24 to allow for 20% attrition due to delivery prior to 48 hours of treatment.

- We will use a repeated measurement ANOVA to compare baseline MAP to MAP at 48 hours, 7 days and weekly thereafter until delivery or 34 weeks.
- Maternal liver toxicity: the proportion of women who develop elevated liver function tests (ALT and/or AST \geq 3x ULN within 24 hours of study drug) will be determined and compared to expected proportion of 20%.
- Descriptive report of proportion of women with
 - Side effects
 - Fetal effects

7.2 **Subject Population(s) for Analysis**

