8.4 Stopping Rules

The study will be stopped under the following circumstances:

- Any maternal or fetal death deemed to be related or possibly related to study participation
- >20% subjects experience liver toxicity (defined as AST or ALT \geq 3x ULN within 24 hours of study drug)

Specific rules to stop study intervention for individual subject

- Delivery, or 34 weeks, which ever occurs first
- Liver toxicity (LFTs \geq 3x ULN within 24 hours of study drug)
- Maternal side effects that cannot be managed with oral medication

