8.6 Data Safety Monitoring Board

The NC TraCS Data and Safety Monitoring Board will serve as the DSMB of record for this single center clinical study. The master protocol has been reviewed and approved. The DSMB monitor safety using *a priori* defined study stopping rules and rules for withdrawal of subjects. The DSMB will review data after every 6 enrolled subjects; the PI will notify the DSMB after every 2 cases of liver toxicity and after every 2 cases of delivery within 48 hours of beginning nicotinamide. The NC TraCS DSMB Charter is available for review.

9 Data Handling and Record Keeping

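### The liver stopping limit is the same 20% that the plan calls expected, so at a true 20% rate the rule would usually stop the study with no excess present

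*Combined protocol and SAP*

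**What the plan says.** Liver toxicity is ALT or AST at or above 3x ULN within 24 hours of study drug. The plan uses 20% for it in two roles.

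- **As the expected rate.** In section 7.1 the observed proportion "will be determined and compared to expected proportion of 20" per cent. The synopsis (Statistical Methodology) says the same.
- **As the study stopping limit.** Section 4.4.1 stops for a prevalence above expectation, "thus > 20% of subjects experience liver toxicity (more than 1 subject for every 5 subjects enrolled". Section 8.4 has only ">20% subjects experience liver toxicity", with no minimum number of women and no evaluation times.

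Section 8.6 adds the only review schedule: "The DSMB will review data after every 6 enrolled subjects". The DSMB works from the a priori "defined study stopping rules and rules for withdrawal of subjects", and is also notified after every 2 liver cases. Section 8.5 has laboratory data reviewed daily.

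Two other places bear on the rate. The list of potential risks in section 8.1 puts liver toxicity under rare (< 1%) at doses up to 3 gm/day. Section 1.4 reports no liver toxicity in 10 phase I women, who took 500 or 1000 mg/day. The protocol gives no source for 20% and no stopping probabilities for the rule.

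**The concern.** A rule meant to detect an excess over an expected rate needs some distance between that rate and the limit, or a probability criterion, because observed proportions scatter around the true one. Here there is neither. If 20% really is expected, crossing the limit is the likely result of an unremarkable study and is not evidence of excess toxicity. If 20% is not expected, the label is wrong in 7.1, 4.4.1 and the synopsis, and the secondary comparison in 7.1 is made against the wrong figure.

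The timing is open as well. Section 4.4.1 counts per 5 women, 8.6 reviews every 6, and 8.4 read alone has no minimum denominator, so one case among the first four women (25%) exceeds it. Whether a study of about 24 women continues could depend on which section is followed.

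**Working it through.** **Inputs.** Limit: observed proportion above 20% (4.4.1, 8.4). Reviews at n = 6, 12, 18, 24 (8.6). Enrolment 24 (3.1, 7.1); the synopsis says 25, which leaves the stopping result unchanged. For power: change of 7 mm Hg, SD 10, alpha 0.05, beta 0.2, n = 20 (7.1).

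**Step 1: the plan's own sample size.** Section 7.1 gives SD 10 for MAP at enrolment and does not state the SD of the change. Assume SD of change = 10 (the same as a within-woman correlation of 0.5, since 10 × √(2 × (1 − 0.5)) = 10) and a two-sided test. A paired t test then has power 79.9% at n = 18, 82.3% at 19 and 84.4% at 20. The stated 20 is reproduced to within one woman, and 20 × 1.2 = 24. The only allowance is for delivery before 48 hours; none is made for a safety stop.

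**Step 2: stopping probability at a true 20%.** The study stops at a review of n women if cases exceed 0.20n, that is at 2 of 6, 3 of 12, 4 of 18 or 5 of 24 or more. At the first review:

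1 − 0.8^6 − 6 × 0.2 × 0.8^5 = 0.345

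An exact binomial recursion through the later reviews gives:

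| Review at n | 6 | 12 | 18 | 24 |
|---|---|---|---|---|
| Cumulative P(stop) | 34% | 51% | 60% | 67% |

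A stop at 24 costs no enrolment, so the share cut short is 60%.

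**Step 3: other readings of the timing, true rate 20%.**

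| When the rule is checked | P(stop) |
|---|---|
| Every 5 women to n = 20 | 52% |
| Once, at n = 24 | 54% |
| Every 6 women (8.6) | 67% |
| After every woman from n = 5 | 73% |
| After every woman from n = 1 (8.4 read alone) | 80% |

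**Step 4: other true rates.**

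| True rate | Every 6 (8.6) | Every woman from n = 1 |
|---|---|---|
| 1% | 0.2% | 4% |
| 5% | 5% | 21% |
| 10% | 21% | 43% |
| 20% | 67% | 80% |
| 30% | 93% | 96% |

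**Step 5: is 20% consistent with the rest of the protocol?** With a true rate of 20%, the chance of no case in 10 women is 0.8^10 = 0.11. That is weak evidence, because the phase I doses were lower. The rare (< 1%) listing is further from 20%, although it describes the agent and not the disease.

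**Step 6: effect on power at a true 20%.** By Step 2 the study ends at n = 6, 12, 18 or 24 with probability 0.345, 0.162, 0.097 and 0.397. Suppose the data are analysed wherever it ends, with 20/24 of the women evaluable (5, 10, 15, 20). The paired-t powers are then 0.228, 0.506, 0.713 and 0.844:

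0.345 × 0.228 + 0.162 × 0.506 + 0.097 × 0.713 + 0.397 × 0.844 = 0.56

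With no attrition the result is 63%. By assumed within-woman correlation:

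| Correlation | 20/24 evaluable | No attrition |
|---|---|---|
| 0.3 | 46% | 53% |
| 0.5 | 56% | 63% |
| 0.7 | 71% | 77% |
| 0.8 | 79% | 85% |

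**The case against.** **The true rate is probably well below 20%.** The risk list and phase I point that way, women with LFTs at or above 2x ULN or HELLP are excluded, and events count only within 24 hours of drug. At 1% to 5% the rule at the DSMB reviews rarely stops the study. This stands, and it makes the 67% conditional on the protocol's own figure. It does not remove the problem, because the plan names 20% as expected and uses it as the comparator. If 20% was meant as a ceiling, the text should say so.

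**Sections 4.4.1, 8.4 and 8.6 are not three rival limits.** Correct: 8.4 restates the 20%, 4.4.1 adds the per-5 wording, and 8.6 is a review schedule. The 80% figure needs 8.4 to be read without 4.4.1. What stands is that no section says when the proportion is evaluated. The DSMB Charter cited in 8.6 may do so, but it is not part of the documents.

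**The rule does discriminate.** Also correct: P(stop) at the reviews rises from 0.2% at a true 1% to 93% at 30%. The weakness is specific to a true rate at or near 20%.

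**Stronger reading on power.** A reader might infer that the study cannot deliver its stated power, with a chance of finishing and detecting 7 mm Hg of only 0.397 × 0.844 = 33%, or 0.331 × 0.844 = 28% if a stop at n = 24 is also counted as failure. The documents do not support this. Enrolment is already complete at n = 24. Section 4.4.1 keeps chart data on women removed from treatment, and 7.2 puts all subjects in the analysis; the 72-hour full data set in 4.4.2 is narrower, but nothing discards data because the study stopped. Sample-size power is also ordinarily stated conditional on no safety stop, so 7.1 is not wrong on that account.

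**A cautious limit in pregnant women is a clinical choice.** Agreed. How strict the limit should be is for the sponsor and DSMB.

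**Conclusion.** The point holds as an inconsistency in the rule. The same 20% is both the expected rate and the limit for exceeding it, with no allowance for chance. At a true 20%, the rule applied at the DSMB reviews stops the study 67% of the time, 60% before full enrolment; other timings give 52% to 80%, and none falls below one half. At lower rates the choice of timing still matters: 5% against 21% at a true 5%.

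The stopping figures assume independent events at a constant rate and are conditional on that rate. They leave out the fetal stopping rule in 4.4.1, which would add to early stopping.

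The effect on power is secondary. If 20% is the true rate and data from a stopped study are analysed, unconditional power for 7 mm Hg is about 56% to 63% with an SD of change of 10, and about 46% to 85% over correlations of 0.3 to 0.8. The 80% in 7.1 should be read as applying if enrolment completes.

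**What to change.** - Reconcile 4.4.1, 7.1, 8.4, 8.6 and the synopsis so that they say whether 20% is the expected rate or the upper limit. Correct whichever label is wrong in light of the phase I result and the rare (< 1%) listing, and give the source of the figure kept.
- State one denominator and one set of evaluation times, tied to the DSMB reviews.
- Print the stopping probabilities of the reconciled rule at several true rates, as in Step 4, so that the sponsor and DSMB set the limit knowing how it behaves.

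This review proposes no limit. The cost is a protocol rewording and a short table.
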